3.2.4. Periocular and Intravitreal Injections

The use of periocular and intravitreal injections during the trial is strongly discouraged, as it hinders the ability to assess the study drugs' effectiveness for controlling inflammation. One injection, either periocular triamcinolone 40mg or intravitreal triamcinolone 4mg, may be administered to treat persistent macular edema during the first 90 days of follow-up if the investigator thinks this is medically necessary. One injection for persistent macular edema is permitted in the first 90 days of follow-up of Phase I, and similarly, one injection treating persistent macular edema is permitted in the first 90 days of follow-up of Phase II. If an injection is given at any time solely for the purpose of treating inflammation, a Protocol Deviation Form should be completed and sent to the Medical Monitor (██████████), Principal Investigator (██████████), and Coordinating Center Manager (██████████). If an injection is given for any reason after the first 90 days of follow-up of either Phase I or Phase II, a Protocol Deviation Form should be completed and sent to the Medical Monitor, Principal Investigator, and

Coordinating Center Manager.

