4.1.2. Phase II: Rescue treatment

In case of the first randomized treatment failure due to intolerability or lack of efficacy within the first six months of treatment, the treatment assignment will be switched to the alternate treatment. At this point, the patient will receive the antimetabolite not originally randomized to and will be followed an additional 6 months or until failure of the second treatment.

Patients will be given 2 weeks to enter into Phase II after treatment failure in Phase I. If patients do not enter within the 2-week window, they should be treated according to best medical judgment of their physician. If the physician believes a patient would benefit from treatment in Phase II, but there is an exceptional circumstance preventing the patient from entering Phase II within the 2-week window, contact the Coordinating Center for assistance.

Guidelines for Visit Schedule II

- Day 1 corresponds to the Baseline-II visit, which is also the first day the patient receives rescue treatment with the medication not initially received. Day 1 may be its own visit date (i.e. if within 2 weeks of the end of Phase I). Alternatively Day 1 may be the same day as the last day of Phase I. All study forms should indicate what visit it is for Phase I and what visit it is for Phase II, if applicable. See the following example below.

Phase	 1	 2								
Visit	 Baseline	 Two weeks	 Non-study visit (treatment failure only)							
Month:	 1	 2	 3	 4	 5	 6	 9	 12		

- Visit dates are determined based on the date of the Baseline-II visit (which may be the same date as Phase I treatment failure), and may not be changed.
- The Baseline-II visit form should be completed to gather information on any changes in health status or medications.
- There should be a minimum of 2 weeks between each study visit.
- Data for the follow-up visits may be collected anytime within the visit window.

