****If not switching on the same day as Phase I treatment failure**

*****Patients will complete this form and bring to the study coordinator for review**

4.3. Phase I Enrollment/Baseline visit

The Phase I Enrollment/Baseline visit should occur after the patient has been screened and determined to be eligible for the study. Screening is a process that should occur before or on the date of the patient's Enrollment/Baseline visit. The baseline eye exam and other baseline assessments may be collected at a separate visit up to 14 days before the patient is enrolled and randomized, with the exception of laboratory measurements which may be collected within 4 weeks or 90 days prior to or on the date of randomization (depending on the test).

Many patients will still have active enough inflammation at the time of enrollment to meet criteria ($\geq 1+$ AC cells, $\geq 1+$ vitreous haze by NEI scale, or active retinal/choroidal inflammation). However, some patients may have had active inflammation when screened (within 14 days prior to enrollment) but at the time of enrollment, the inflammation is improved because of steroid treatment. As long as the inflammation met inclusion criteria within this 14 day period, those values can be used for the baseline exam (enrollment exam). If there is a patient whom you think is very likely to be enrolled in the next 14 days but you are still waiting for some screening labs, it is fine to go ahead and consent and obtain the baseline study assessments (eye exam with secondary grader using both NEI and Miami scales for vitreous haze, fundus photos, OCT, questionnaires, etc.), as long as you do not randomize. Randomization can only occur once all eligibility criteria have been verified. The inflammation recorded on the baseline Clinical Eye Exam form needs to meet inflammation eligibility criteria.

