3.5.1 Injections

If a patient receives a corticosteroid injection 90 days after enrollment, it is not possible to truly assess the study drug's ability to manage inflammation at the Month 6 visit. Therefore, as a sensitivity analysis, the primary outcome for these patients will be considered by the inflammation levels at the time of the injection. If the patient received the injection because of uncontrolled inflammation, the patient will be considered a treatment failure. If the patient met the definition of treatment success at the time of the injection, the patient will be considered a treatment success.

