4.1 Summary

The following analysis populations are planned for this study:

- The **screening population**, which is to include all patients who are screened for participation in the trial.

- The **safety population**, which is to include all patients who receive any amount of planned study medication (mycophenolate mofetil or methotrexate).
- The **intent-to-treat efficacy population**, which is to include all patients who are randomized. This is the primary population for the efficacy analyses.
- The **per-protocol efficacy population**, which is to include all patients in the intent-to-treat efficacy population, excluding patients with any of the following: (a) major protocol deviations, or (b) noncompliance with study medications (less than 50% of the study drug received by self report or pill counts at study visits).

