4.2 Major protocol deviations

The incidence of deviations from the inclusion and exclusion criteria will be summarized using counts and percentages, and the treatment groups compared for the overall frequency of deviations using a $2 \times N$ Fisher's exact test. Similar deviations will be grouped into general categories of deviations for a more condensed summary. A listing of deviations by participant will also be produced. Any major deviations from the protocol will be listed and/or summarized, including, but not limited to, participants who:

- never received study drug
- were subsequently found to be ineligible for the study
- never returned for a follow-up visit
- have follow-up visits outside the prescribed visit window
- received a corticosteroid injection >90 days after enrollment for macular edema or at any time for inflammation

The number and percentage of randomized participants actually receiving study medication, permanently discontinuing study drug (subdivided by reason), and receiving injections >90 days past enrollment will be summarized. A summary of study participants randomized by site will also be provided. Treatment groups will be compared for the proportion and reason for study drug discontinuation using the chi-square test. A summary of participant status at the end of the study period will also be generated with categories including lost to follow-up.

5 Data Collection and Quality Assurance

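### The SAP counts the 90-day injection limit from enrollment, so an injection the protocol permits in Phase II can be a major deviation and remove the patient from a per-protocol population that is not defined by phase

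*Combined protocol and SAP*

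**What the plan says.** **Protocol.** Section 3.2.4 allows one injection for persistent macular edema in the first 90 days of Phase I. It then says that "one injection treating persistent macular edema is permitted in the first 90 days of follow-up of Phase II". A deviation form is required for any injection given solely for inflammation. It is also required by the clause beginning "If an injection is given for any reason after the first 90 days of follow-up of either Phase I or Phase II". The limit for macular edema thus runs separately in each phase. Section 4.1.2 fixes the start of the Phase II count: "Day 1 corresponds to the Baseline-II visit, which is also the first day the patient receives rescue treatment". Section 4.3 ties enrollment to the Phase I baseline: "The Phase I Enrollment/Baseline visit should occur after the patient has been screened and determined to be eligible for the study".

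**SAP.** Section 4.2 counts as a major deviation having "received a corticosteroid injection >90 days after enrollment for macular edema or at any time for inflammation", with no Phase II clause. The summary promised in the same section, which covers randomized participants, uses the same clock: "receiving injections >90 days past enrollment will be summarized". Section 4.1 forms the per-protocol population from the intent-to-treat population, "excluding patients with any of the following: (a) major protocol deviations" or with less than 50% adherence. It defines one such population and does not divide it by phase or aim.

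**The concern.** Two separate faults meet here.

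First, the SAP classifies as a major deviation something the protocol expressly permits. Patients who followed the protocol in Phase II would be dropped from any Aim 2 per-protocol analysis.

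Second, because the per-protocol population has no time limit, an event after the Aim 1 outcome is fixed can decide whether a patient counts in an Aim 1 per-protocol analysis. Only Phase I failures enter Phase II, so the clock mismatch by itself can remove only failures. The Aim 1 analysis is also scheduled for when all patients have completed month 6 (SAP 3.11). At that point, Phase II injections are known for early enrollees and largely not for late ones, so membership would depend partly on the date of enrollment.

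At stake is how far a per-protocol result can be trusted as a check on the intent-to-treat result.

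**Working it through.** **1. When the two clocks disagree.** Let Phase II start *t* days after enrollment. The permitted Phase II window runs from day *t* to day *t* + 90. The share of it lying more than 90 days after enrollment is min(1, *t*/90).

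| Phase II starts | Permitted window (days from enrollment) | Share classed as major deviation |
|---|---|---|
| day 30 | 30–120 | 33% |
| day 60 | 60–150 | 67% |
| day 90 | 90–180 | 100% |
| about day 183 (month-6 failure) | 183–273 | 100% |

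Injections for inflammation are not in dispute: both documents treat them as deviations at any time.

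**2. Who is exposed.** SAP 3.4.2 takes 108 randomized per arm, 90% retention, and Aim 1 success of 40% and 60% (methotrexate and mycophenolate in SAP 3.4.1).

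- Retained per arm: 108 × 0.9 = 97.2
- Failures, 40% arm: 97.2 × 0.6 = 58.3
- Failures, 60% arm: 97.2 × 0.4 = 38.9

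These reproduce the SAP's expected Phase II enrollment of 58.3 and 38.9.

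**3. Size under assumed injection rates.** The documents give no Phase II injection rate, so the rates below are assumptions. The illustration also assumes that every failure enters Phase II, that every injection is caught by the enrollment clock, that no successes are removed, and that there are no other per-protocol exclusions. If a fraction *f* of failures is removed and planned success is *s*, per-protocol success is *s* / (1 − *f*(1 − *s*)).

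| Failures removed, methotrexate / mycophenolate | Methotrexate success | Mycophenolate success | Difference |
|---|---|---|---|
| none | 40% | 60% | 20 points |
| 10% / 10% | 0.4/0.94 = 42.6% | 0.6/0.96 = 62.5% | 19.9 |
| 20% / 10% | 0.4/0.88 = 45.5% | 62.5% | 17.0 |
| 10% / 20% | 42.6% | 0.6/0.92 = 65.2% | 22.7 |

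In the 10% / 10% row about 5.8 and 3.9 patients are removed. Equal rates raise both proportions and leave the difference almost alone. A material shift in the difference needs unequal rates.

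**4. Adding removed successes.** Phase I successes stay on study drug to month 12, and any injection in months 6–12 is more than 90 days after enrollment. SAP 4.1 and 4.2 as worded remove those patients too. If a fraction *g* of successes is removed, success becomes *s*(1 − *g*) / [*s*(1 − *g*) + (1 − *s*)(1 − *f*)].

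- *f* = *g* = 10%: success stays at exactly 40% and 60%.
- *f* = 10%, *g* = 20%: 0.32/(0.32 + 0.54) = 37.2% and 0.48/(0.48 + 0.36) = 57.1%, so both fall.

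The direction therefore depends on two unknown rates.

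**The case against.** The strongest reply is that little rests on this population. SAP 4.1 makes intent-to-treat primary, SAP 3.5 makes complete cases the primary method for missing outcomes, and no listed analysis for either aim is assigned to the per-protocol set. SAP 6.1 promises only the number of subjects in each population. This stands, and it limits the harm to an analysis that the SAP makes possible but does not specify.

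The illustration is also generous. Laboratory serious adverse event failures do not switch, some patients may decline, entry normally closes after two weeks, early failures are only partly caught, and the protocol strongly discourages injections. This stands too: the percentages are not forecasts.

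A narrower reading is possible. The list in SAP 4.2 is introduced as deviations from the protocol, and a permitted injection is not one. SAP 3.4.2 also speaks of enrollment into rescue therapy. Neither settles the matter. The list item names its own clock, the summary in the same section refers to randomized participants and enrollment, and the protocol ties enrollment to the Phase I baseline.

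A reader might go further and infer that the rule removes only failures and so inflates Aim 1 success. The documents do not support that. Only the clock mismatch is confined to failures; the rule without a phase limit also reaches successes injected in months 6–12.

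A reader might also take SAP 3.5.1, which opens "If a patient receives a corticosteroid injection 90 days after enrollment", as the same error. It is a sensitivity analysis of the Month 6 outcome. For Phase I its clock agrees with the protocol, and it excludes no one.

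**Conclusion.** The contradiction is explicit and holds on the current text. SAP 4.2 makes a permitted Phase II macular edema injection a major deviation whenever it falls more than 90 days after enrollment, and SAP 4.1 carries that into a single per-protocol population. Separately, events after the Aim 1 outcome can change Aim 1 per-protocol membership, with a bias whose direction cannot be determined from the documents.

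The primary test, the intent-to-treat population and the sample size are untouched. Under the assumptions stated in the working, the difference of 20 points barely moves with equal 10% removal and ranges from 17.0 to 22.7 points when removal is 20% in one arm and 10% in the other. The point is worth correcting because the rule as written misclassifies compliant patients. It does not threaten the main result.

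**What to change.** 1. Reconcile protocol 3.2.4 with SAP 4.2, so that the SAP classifies an injection as a deviation by the clock the protocol applies in each phase. The summary of late injections in SAP 4.2 should use the same clock. This concerns classification for analysis only; no view is taken on when injections should be allowed.
2. In SAP 4.1, define two per-protocol populations: one for Aim 1 (months 0–6) and one for Aim 2 (Phase II). Each should use only deviations and adherence within its own period.
3. In SAP 3.5.1, add a note on which baseline applies if that sensitivity analysis is reused for Aim 2. No change to the success rule in protocol 2.5.1 is proposed.

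The cost is a wording amendment, best made before the unmasked final analysis. It changes no visit or sample size.

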5.1 Quality assurance and security

Data collection forms, training, security, and quality assurance are discussed in the Manual of Operations for the FAST Treatment Trial.

5.2 Analysis sets

Data sets for analysis will be produced at the [REDACTED] central site by database manager [REDACTED]. Each will be a Microsoft Excel® worksheet containing a single header line whose variable names match the Access database. Each analysis set will be in the form of a rectangular table in which

each column corresponds to a single variable and each row to an observation. All missing values will be coded explicitly using the string **NA** (as used in the R software). Codes for categorical variables (such as 1 for male, and 2 for female) will be avoided in favor of self-documenting character strings (such as Male, Female) whenever possible. Automated checks will be made to ensure consistency and that each variable in the analysis set has in-range values (protecting against negative ages, spelling errors in categorical factors, and similar errors).

A detailed codebook will be prepared, containing for each variable, (a) the form from which the variable derived, (b) the text of the question, (c) all possible values for the variable, and (d) summary statistics for the variable. Note that all codes and character strings that represent categorical factors will be clearly defined in the codebook. Units for each continuous variable (e.g. central subfield thickness, logMAR) will be unambiguously indicated for each variable. Each release of the analysis set will be accompanied by the corresponding version of the codebook. Version numbering with dates will be strictly observed. Standard report-generation software included with the R statistical and data analysis package will be used to ensure consistency of the codebook and analysis set at all times.

5.3 Data monitoring reports

Data monitoring reports will be prepared based on analysis data sets. These will be prepared using report-generation software. Monitoring reports will include (a) recruitment reports for each site, (b) compliance reports, (c) retention reports, and (d) data quality reports. These will be reviewed at the central site on a monthly basis, and communicated to the study sites on a monthly basis.

6 Human Subjects

6.1 Summary of final dispositions

All subjects who provide informed consent will be accounted for in this study. The frequency of subjects in each population will be presented. We will also present the frequency of subjects in each subgroup, the frequency of withdrawal and loss to follow-up, and any major protocol violations.

6.2 Data and Safety Monitoring Committee

6.2.1 Scope

A Data and Safety Monitoring Committee (DSMC) will be empaneled by the NEI. We propose that this committee consist of 5-7 individuals, and should include (a) uveitis specialists, (b) an independent biostatistician, (c) a bioethicist, and (d) a member to protect the interest of the Indian population. The committee will meet in person at least once per year. *Ad hoc* meetings as needed may also be convened. All study protocols will be subject to review and approval by Institutional Review Boards at [REDACTED], and by the DSMC.

The Data and Safety Monitoring Committee will meet to review the interim efficacy data when primary outcome data are available on approximately one third of the study subjects—approximately 6 months after the 72nd subject has been enrolled in the trial (as discussed above in Section 3.10), and when data are available on approximately 2/3 of subjects. The DSMC will make one of the following recommendations:

- Continue the trial without modifications
- Continue the trial with study modifications
- Terminate enrollment or treatment in the trial because of safety concerns
- Terminate enrollment or treatment in the trial because of efficacy

6.2.2 Meetings

All in-person and teleconference meetings of the DSMC and study personnel will consist of (a) “open” sessions, which may be attended as needed by masked study personnel, and (b) “closed” sessions, which may only be attended by unmasked study personnel [REDACTED] and (c) “closed” sessions attended only by the DSMC personnel. Care will be taken so that *no* treatment assignments, data which would allow treatment assignments to be determined, or outcome data based on treatment assignments will be revealed during the open sessions.

The DSMC will be unmasked. Closed reports will tabulate baseline covariates, adverse events, and outcomes by treatment assignment and study site. Written closed reports will always use the labels Treatment A and Treatment B for increased information security. However, the DSMC will know which drug corresponds to which label.

Interim reports for the DSMC will be prepared by the central [REDACTED]. These reports will include (a) recruitment overall, and by study site, (b) compliance, and (c) retention. The reports will also list study outcomes, and all adverse outcomes, including deaths. The DSMC will determine the database closure dates for each report in advance; archival copies of the (a) main REDCap database, and (b) study analysis file as they exist at the time of each report will be maintained.

All reports will be sent using secure email to the members of the DSMC two weeks prior to each meeting (or more, if desired by the DSMC).

Each printed (hard copy) interim report will be labeled clearly as confidential, bound so that the contents are not visible from the outside, and labeled with the name of each person authorized to receive it. Reports will be kept in possession of [REDACTED] and only delivered in person or by encrypted email; reports not delivered due to absences are to be shredded. In addition, redacted versions of the interim reports will be prepared which contain no masked study information, and which are suitable for restricted distribution to other personnel on an as-needed basis. All hard copies will be destroyed at the end of each meeting, except for a copy to be kept in a locked file cabinet accessible only to [REDACTED].

6.2.3 Decisions

The DSMC will make decisions with the benefit of prespecified decision guidelines. These guidelines will be agreed upon at the initial meeting, and are expected to include (a) safety, (b) efficacy, (c) clinical importance, (d) effect of baseline covariates, or (e) validity.

Benefits. Unmasked interim analyses (See Section 3.10) will be conducted to determine whether or not sufficient evidence has accumulated to justify stopping the trial because one treatment is clearly superior (and therefore should be extended to all future cases). The guidelines for efficacy will use group sequential boundaries for judging the statistical significance of the primary outcome measure. The Lan and DeMets flexible alpha spending approach will be used.

Early discontinuation in this trial has the following disadvantages. First, early discontinuation will make it more difficult to assess homogeneity of study sites. In this trial, where the majority of planned enrollment is not from the US, discontinuation at time $t=1/3$ for instance would occur when only 15 American patients had been enrolled (under our enrollment projections), and at $t=2/3$, only 30 American patients. Reflection on these small numbers of American patients may limit the adoption of the results of the trial. Second, early discontinuation reduces the power to assess the secondary aims of Specific Aim 1, and for Specific Aim 2. For these reasons, we propose to use conservative stopping rules.

We propose to use a Hwang-Shih-deCani alpha spending function of the form

$$\alpha^*(t) = \frac{\alpha(1 - e^{-\gamma t})}{1 - e^{-\gamma}}$$

with γ chosen to be equal to -5.623626 exactly. This value was chosen to make the alpha at $t=1/3$ approximately equal to 0.001. The resulting alpha at $t=2/3$ is approximately 0.0075. The R package `gsDesign` (v. 2.7-04 or higher) will be used for selected analyses.

The proposed plan is to have two interim looks, at approximately $t=1/3$ and $t=2/3$ (one third and two-thirds through the study), with the specific fractions to depend on the total available data at face to face DSMB meetings.

The use of a flexible alpha-spending function protects the 0.05 alpha level of the overall trial while allowing for additional interim analyses for efficacy (if needed), without specifying the number and timing of the analyses at the start of the study. We note that the alpha spending function, including the value of γ , cannot be changed once the trial has begun.

Harm. Stopping for harm will be done at the judgment of the DSMC. Several endpoints will be examined, including serious adverse events such as significant and sustained laboratory abnormalities as described in the protocol, or mortality. While the analysis would consider maldistribution of predictive factors such as age, it is recognized that ethical considerations require careful considerations of statistical tests as well as qualitative judgments in the light of experience. Any additional analyses required by the DSMC will be conducted by [REDACTED], as needed.

Note that serious adverse events (SAE) are reported directly to the medical monitor [REDACTED] within 24 hours of the time the study site learns of them, and the medical monitor will subsequently pass this information on to the DSMC Chair. The medical monitor will receive

notification of the event, the timing of the event, a medical narrative from the study site, the site location, and the patient identification number. The statistician will report the study treatment assignment to the DSMC Chair if deemed necessary by the DSMC. If use of either drug use clearly results in an unacceptable increase in the risk of treatment failures, then the study will be stopped. It is difficult to fully prescribe boundaries for monitoring safety because there need not be strong evidence to discontinue the study if it appears that the treatment is harmful.

Futility. Early discontinuation due to the unlikeliness of significant findings conditional on interim results would prevent the analysis of Specific Aim 2 and of the secondary aims of Specific Aim 1. No stopping rules based on futility or conditional power calculations are included in the trial plan.

7 Safety and tolerability

The analysis of safety in this study will include summaries of the following:

- Exposure
- Adverse events
 - Adverse events and serious adverse events (including deaths)
 - Adverse events leading to withdrawal
 - Any deaths

